#### **4. Interim Analyses**

Interim analyses of study data are planned according to the alpha spending rule [Lan and DeMets, 1994]. The proportion of expected events (i.e., self-reported non-fatal overdose) is considered as the information statistic. The  $p$ -values will be constructed to maintain the overall study power of 0.05, two-sided. If the test statistic exceeds the boundary, then the study could be considered for early termination due to emerging differences between the two arms. The PI shall recommend to the Data and Safety Monitoring Board (DSMB) that two interim analyses be conducted over the course of the study. One would be conducted early on during the trial (e.g., once approximately one-third of the target sample size has been recruited and followed out to 12 months) to assess potential harms, and a second interim analysis would be conducted later on (after approximately two-thirds of the target sample size has been enrolled and followed to 12 months) to assess for benefit/efficacy.

#### **5. Study Stopping Rules**

The study investigators will report all adverse events and significant adverse events to the DSMB. Moreover, all adverse and significant adverse events will be summarized by the study biostatistician monthly for the first six months and then each quarter. These reports will be reviewed and commented on by the DSMB, which may recommend early termination of the trial given evidence of harm based on these and other safety data. Note that, since the study outcome (e.g., self-reported overdose) is defined as an SAE, these events are unblinded to the study biostatistician, principal investigator, and DSMB as they are reported.

We do not propose that the trial be stopped for futility, as additional information collected at the 12-month follow-up may be useful for public health program planning & practice. However, early evidence of efficacy from the second planned interim analysis may provide justification for the DSMB to recommend stopping the trial early. Analysis of efficacy in the second interim analysis will be undertaken as described above.

Finally, the entire trial will stop if any investigator judges it necessary for medical, safety, regulatory, or other reasons consistent with applicable laws, regulations, or good clinical practice. Once a concern of this proportion is raised, the decision to stop the trial will be made through immediate consultation with the IRB, the DSMB, and NIDA.

Additionally, should research come out during the RAPIDS trial that demonstrates increased risk of using fentanyl test strips, the RAPIDS trial may be changed or stopped.

#### **6. Sample Size Calculations**

We provide power calculations for key outcomes below, based on an enrollment of 500 participants (n=250 per arm). To ensure we have a sufficient number of participants and to account for attrition,

we have received IRB approval to enroll up to 550 if necessary. The following assumptions are based on findings from our pilot intervention study. First, at baseline, 37% of participants reported a lifetime history of overdose, and 11% reported an overdose in the past six months. As such, for the primary analyses, we assumed that 20% of participants in the control arm will experience an overdose during the 12-month follow-up period. Second, we conservatively assumed an 80% retention rate in the trial, although we were able to retain 90% of pilot participants.

Given these assumptions, we have >80% power to detect a 50% reduction in overdoses. Similar effect sizes were assumed for an ED-based overdose prevention intervention, and have been deemed as a benchmark for success by key stakeholders. For the exploratory endpoint in Aim 1 (time to first fatal overdose or suspected overdose resulting in an EMS record), we conservatively assumed that only 38% of self-reported overdoses would result in death or attendance by EMS, based on previously published data, for a rate of 8 per 100 person-years in the control arm. We have  $\geq 80\%$  power to detect a 50% reduction in the hazard of fatal overdose or ED visit for an overdose.

Finally, we used a method to estimate sample size for evaluating mediation by joint testing of both links in an indirect pathway from exposure to mediator to outcome (Aim 2). Given the assumptions described above, we have >80% power to detect a statistically significant mediated effect for a coefficient for exposure on mediator and mediator on outcome of at least 0.8 (i.e., a relative risk of  $\exp[0.8] \cong 2.3$ ), respectively.

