Experimental arm participants will receive the RAPIDS intervention, which includes education about the dangers of IMF, motivational interviewing to increase willingness to use fentanyl test strips and engage in overdose risk reduction behaviors, hands-on training to use the test strips, and opportunities to plan and role- play how to implement overdose risk reduction behaviors upon receipt of a positive or negative test result. In addition, intervention participants will receive ten test strips for personal use. Motivational interviewing “booster” sessions will occur at 1, 2, and 3 months post-randomization, with additional test strips provided on an as needed basis. In the attention-matched control arm, participants will receive standardized overdose education and naloxone distribution (OEND) training, with attention-control visits at 1, 2, and 3 months.

Participants in both arms will receive a naloxone kit after completion of the first session, and information regarding where to obtain additional naloxone at subsequent visits. Follow-up interviews will occur at 6 and 12 months. The primary endpoint will be the rate of self- reported overdose over the follow-up period. Secondary endpoints (e.g., accidental overdose death and suspected EMS runs for overdose) will be ascertained by data linkage to statewide overdose surveillance databases maintained by the research team. Consistent with recruitment rates in our prior studies, we aim to enroll 20 participants per month starting in Year 1 until target

enrollment is reached.

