### **3.1f Analytic Plan**

**Assessing intervention efficacy in reducing emergency department (ED) presentation for an overdose or overdose death (Aim 1, secondary endpoint).** First, we will compare the overall rate of patients experiencing this composite outcome over the 12-month follow-up period in each group. Next, we will examine the time to first ED presentation or death using a Kaplan-Meier analysis. Patients will be censored as of the first date of either of these outcomes or at the end of the 12-month period. We will use Breslow's method to test if the time to either outcome differs between the groups, since this approach gives greater emphasis to shorter time elapsed after the intervention, which has greater clinical significance. Third, Cox proportional hazards modeling will be used to estimate hazard ratios for the treatment effect. Multivariable models will be constructed to adjust for possible post-randomization confounding.

**Examine whether the treatment effect is mediated by differential uptake of risk reduction behaviors in the intervention arm (Aim 2).** If the RAPIDS intervention shows efficacy in reducing overdose rates among the sample (Aim 1), we will explore the extent to which this relationship works through several possible mediators (see Figure 4). For mediation analyses, first, we will examine, in multivariable regression models, which mediators, if any, are significantly changed by the intervention (i.e., the rate of change differed by treatment

---

 <https://rc.partners.org/research-apps-and-services/collect-data#redcap>

Brown University IRB Original Approval: 4/18/2019  
Brown University IRB Amendment Approval: 11/22/2019  
Brown University IRB Amendment Approval: 8/10/2020  
Brown University IRB Amendment Approval: 10/15/2020  
Brown University IRB Amendment Approval: 02/26/2021  
Brown University IRB Continuing Review Approval: 03/18/2021  
Brown University IRB Amendment Approval: 06/15/2021  
Brown University IRB Amendment Approval: 09/01/2021  
Brown University IRB Amendment Approval: 10/05/2021  
Brown University IRB Amendment Approval: 11/09/2021  
Brown University IRB Amendment Approval: 12/13/2021

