### **Power Calculation and Sample Size**

We are seeking IRB approval for  $n=550$  participants enrolled in the study. We provide power calculated for key outcomes below, based on an enrollment of 500 participants ( $n=250$  per arm) to account for attrition. The following assumptions are based on findings from our pilot intervention study. First, at baseline, 37% of participants reported a lifetime history of overdose, and 11% reported an overdose in the past six months. As such, for the primary analyses, we assumed that 20% of participants in the control arm will experience an overdose during the 12-month follow-up period. Second, we conservatively assumed an 80% retention rate in the trial, although we were able to retain 90% of pilot participants.

Given these assumptions, we have >80% power to detect a 50% reduction in overdoses (i.e., the primary endpoint for Aim 1, see Research Strategy section C.9, Figure 6A). Similar effect sizes were assumed for an ED-based overdose prevention intervention, and have been deemed as a benchmark for success by key stakeholders. For the second endpoint in Aim 1 (time to first fatal overdose or ED visit related to an overdose), we conservatively assumed that only 38% of self-reported overdoses would result in death or presentation to

the ED based on previous published data, for a rate of 8 per 100 person-years in the control arm. As

Brown University IRB Amendment Approval: 11/09/2021

Brown University IRB Amendment Approval: 12/13/2021

Brown University IRB Amendment Approval: 11/09/2020

Brown University IRB Amendment Approval: 11/22/2019

Brown University IRB Amendment Approval: 8/10/2020

Brown University IRB Amendment Approval: 10/15/2020

Brown University IRB Amendment Approval: 02/26/2021

Brown University IRB Continuing Review Approval: 03/18/2021

Brown University IRB Amendment Approval: 06/15/2021

Brown University IRB Amendment Approval: 09/01/2021

Brown University IRB Amendment Approval: 10/05/2021

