At the completion of the study, patterns of data missingness will be explored to determine the appropriate assumptions required for each affected variable. Missing covariate data considered to be missing completely at random (MCAR), missing at random (MAR) and/or missing not at random (MNAR) will be handled using multiple imputation in SAS (proc MI procedure). Performed in two stages using chained equations, the model will specify the conditional models for the missing outcome and covariates as "MCAR", "MAR", or "MNAR". First, missing patterns will be tested. Then, imputing procedures will be separated into an "imputation phase", "analysis phase" and a "pooling phase". Finally, models with complete case, available data, and fully imputed data will be compared based on their coefficients, standard errors (SE), and *p*-value for the covariates included in the model.

To examine the effect of missing self-reported outcome data on the results, we will first examine the concordance between the self-reported outcome and the primary endpoints relying on administrative data linkages. If a high degree of correlation is observed (e.g.,  $r > 0.80$ ), we will assume missing self-reported outcome information has a negligible impact on the results. If a lack of concordance is observed, we will conduct stratified analyses by number of completed outcome visits (e.g., zero, one, and two) and also employ imputation-based procedures as noted above.

Second, in an exploratory analysis, we will determine the effect of the intervention on the more severe overdose endpoints, defined as an EMS run for suspected overdose, an ED encounter for drug overdose, or drug overdose death. An unintentional fatal overdose (involving any substance) will be determined through linkage to the Office of the State Medical Examiner (OSME), which is responsible for investigating all accidental deaths. Specifically, as defined previously, cases will be considered confirmed unintentional drug-related overdose fatalities if: (i) the death was pronounced in Rhode Island; (ii) the final manner of death was deemed an accident by the medical

---

 <https://doi.org/10.1016/j.drugpo.2017.05.029>

examiner, and (iii) a drug is listed on the death certificate as the primary cause of death or a significant contributing factor. This analysis will be conducted using the same methodology as described above.

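### SAP section 6 gives a rate and a power for two different event sets, neither of them the severe-overdose endpoint the SAP will analyse, and the stated 80% power does not follow from its own inputs

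*SAP*

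**What the plan says.** Within the SAP, three event sets stand for one endpoint.

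- Section 3 (Aim 1) defines the exploratory severe-overdose analysis as "an EMS run for suspected overdose, an ED encounter for drug overdose, or drug overdose death". It is to use the same methods as the primary analysis, whose follow-up ends 15 months after baseline.
- Section 6 names the endpoint as "time to first fatal overdose or suspected overdose resulting in an EMS record" and derives the rate of 8 per 100 person-years by assuming that "only 38% of self-reported overdoses would result in death or attendance by EMS".
- The next sentence of section 6 claims at least 80% power for a "50% reduction in the hazard of fatal overdose or ED visit for an overdose".

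The protocol differs again. Section 3.1f, Analytic Plan, is headed as "reducing emergency department (ED) presentation for an overdose or overdose death (Aim 1, secondary endpoint") and ends follow-up at 12 months. The power section of the Data and Safety Monitoring Plan (Attachment F, A1) also uses death or ED visit. It reaches the same 8 per 100 person-years by assuming that "only 38% of self-reported overdoses would result in death or presentation to" the ED. It refers for the power to Figure 6B in a section C.9, which is not in the supplied text.

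**The concern.** A rate, a power statement and an analysis should concern the same event. Here the rate is for death or EMS, the power for death or ED, and the analysis for all three. Who counts depends on the section followed. Someone attended by EMS but not taken to the ED counts in SAP section 3 and in the rate, but not in the power sentence or in protocol 3.1f. Someone who reaches the ED without EMS counts in SAP section 3, the power sentence and protocol 3.1f, but not in the rate.

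Nor are the two sources interchangeable on the SAP's own terms. Its EMS component rests on a case definition for suspected opioid overdose, its ED component is any accidental drug overdose, and the trial admits people whose only qualifying use is stimulants.

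At stake are the event set, the follow-up end and the status of the only Aim 1 endpoint built entirely on administrative records. So is a power figure that readers may rely on when they interpret a null result.

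**Working it through.** **Inputs**

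- Control-arm overdose risk 20% over 12 months; share 38%; rate 8 per 100 person-years; 50% hazard reduction (HR 0.5); 500 enrolled, 250 per arm; 80% retention, so 0.8 × 250 = 200 per arm (all SAP section 6).
- Two-sided 0.05 (SAP section 4, where it is called power; section 6 gives no alpha).
- Follow-up T of 1 year (SAP section 6, protocol 3.1f) or 1.25 years (SAP section 3).

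**The plan's own figures first.** The rate reproduces: 0.20 × 0.38 = 0.076, rounded to 8 per 100 person-years. The primary power statement also reproduces. For 20% against 10% with 200 per arm, power = Φ[(√200 × 0.10 − 1.96 × √(2 × 0.15 × 0.85)) / √(0.16 + 0.09)] = Φ(0.849) = 80.2%.

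**Expected events for the severe endpoint.** With rate r and n per arm, d = n(1 − exp(−rT)) + n(1 − exp(−0.5rT)).

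- n = 250, T = 1: 250 × 0.0769 + 250 × 0.0392 = 29.0.
- n = 250, T = 1.25: 250 × 0.0952 + 250 × 0.0488 = 36.0.

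**Power (Schoenfeld).** Power = Φ(√(d/4) × ln 2 − 1.96).

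| Per arm | 12 months | 15 months |
|---|---|---|
| 250 | 29.0 events, 46% | 36.0 events, 55% |
| 200 | 23.2 events, 39% | 28.8 events, 46% |

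**Events needed for 80%.** 4 × (1.96 + 0.842)² / (ln 2)² = 65.3, so 66 (Freedman's formula gives 71). At 8 per 100 person-years, that takes about 1,140 participants at 12 months or about 920 at 15 months.

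**Attempts to rescue the stated figure.** At 250 per arm and 12 months, Freedman's formula gives 43%, a two-proportion test 44%, and a one-sided test 59%. The most favourable combination tried was 275 per arm, 15 months, one-sided, with the rate raised to −ln(0.8) × 0.38 = 8.48 per 100 person-years. It gives about 72%.

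**Effect of the definition.** The union of EMS, ED and death contains both subsets, so its rate is at least as high as either. The documents give no union rate. As an assumption, with 250 per arm:

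| Assumed union rate per 100 person-years | 12 months | 15 months |
|---|---|---|
| 8 | 46% | 55% |
| 10 | 55% | 64% |
| 12 | 62% | 71% |
| 15 | 71% | 80% |
| 20 | 82% | 89% |

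Power of 80% needs about 18.8 per 100 person-years at 12 months or 15.1 at 15 months. On the plan's own conversion, that is 18.8/20 = 94% or 15.1/20 = 76% of overdoses meeting the endpoint, against the 38% assumed.

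**The case against.** The strongest reply is that the SAP's analysis section gives one clear definition, that the SAP calls the endpoint exploratory, and that the differences from the protocol look like later development. The SAP's EMS case-definition link carries the year 2022, while the last protocol approval shown is December 2021. That lowers the weight of the point and may explain the gap between the documents. It does not explain why consecutive sentences of SAP section 6 describe different events.

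Four stronger readings are tempting, and the documents do not support them.

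- A reader might infer that the mixed components cause the power shortfall. They do not. Moving to the union can only hold or raise the rate, and the shortfall is present under any single fixed definition at 8 per 100 person-years.
- A reader might say that the 38% cannot describe both ED presentation and EMS attendance. Both documents present it as a conservative planning value, which could be applied to two overlapping events. What its source measured is not visible here. The fair criticism is that the label changed and the number did not.
- A reader might count protocol 3.1a, which mentions "accidental overdose death and suspected EMS runs for overdose", as a further composite. That text is a list of examples of secondary endpoints, so it neither defines a composite nor excludes ED visits.
- A reader might put a size on the definitional spread. That needs the share of EMS-attended people who do not reach the ED, and the share reaching the ED without EMS. Neither is given.

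Figure 6B might rest on other assumptions and could not be checked. The rate, effect and enrolment tested here are those printed beside the claim.

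**Conclusion.** The point holds in two separate parts. First, the rate and the power in SAP section 6 belong to two event sets, and neither is the endpoint analysed in SAP section 3. The protocol's analytic plan adds a different status and follow-up end. Second, and independently, power of at least 80% is not delivered by the stated inputs. It is about 46% at 12 months and 55% at 15 months with 250 per arm, or 39% and 46% with 200 per arm, on 23 to 36 expected events against about 66 needed.

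These figures assume exponential event times, proportional hazards, two-sided 0.05 with no adjustment for interim looks, and full follow-up of those counted. A union rate above 8 would improve them, but no document supports the 15 to 19 per 100 person-years that 80% power would take. The primary endpoint's sample size is untouched, so this is a correction that should be made and not a threat to the main result.

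**What to change.** Use the three-part definition of SAP section 3 in SAP section 6, protocol 3.1f and the Attachment F power section, with one follow-up end and one status, secondary or exploratory. Attach the 38% only to the event its source measured. Then choose one of three treatments of the power claim:

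- replace it with the recomputed figure at 8 per 100 person-years (about 46% at 12 months, 55% at 15);
- give a range over stated, assumed union rates, such as 10 per 100 person-years (55% and 64%) and 15 (71% and 80%);
- drop it for this endpoint.

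Report EMS, ED and death separately as components, so that the reader can see which source drives the result.

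The cost is wording changes in both documents and one recalculation, which must rest on an assumed union rate because none is given. Unless the claim is dropped, the stated power becomes less favourable. No extra trial data are needed.

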#### Assessing intervention efficacy in reducing fatal and nonfatal overdose (Aim 1, primary endpoint).

The primary outcome will be **non-fatal overdose**, defined as a composite outcome, consisting of one of the following:

1. A self-reported overdose ascertained at the six and/or 12 month follow-up visits;
2. A non-fatal opioid overdose identified in the Rhode Island EMS database, using a case definition for suspected overdose developed by RIDOH previously;
3. An emergency department encounter for an accidental drug overdose that did not result in death, using a case definition developed by the CDC;

The primary analysis will be conducted using a survival framework, with time to *first* nonfatal overdose—identified through any of the data sources noted above—serving as the primary outcome. For self-reported data, event times will be estimated from SAE reports (in which participants are asked to estimate the date of their overdose). Participants will be right-censored as of the date of the first

---

 <https://www.ncbi.nlm.nih.gov/pmc/articles/PMC7948191/>

outcome event or at the end of the follow-up period, defined as 15 months following the participant's baseline visit.

To account for potential imbalance and to improve statistical efficiency, we will adjust for known or anticipated prognostic variables measured at baseline. These variables will include sociodemographic characteristics (e.g., age, gender identity, race/ethnicity), recent criminal justice involvement, housing instability, and substance use patterns including injection drug use & history of overdose. Variables will be transformed or categorized as necessary to address skewed or imbalanced data. We will also adjust for pre-baseline EMS runs for suspected opioid overdoses and ED encounters for drug overdoses using the case definitions noted above, occurring up to six months prior to the date of the participant's baseline visit.

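### The claimed power of at least 80% for severe overdose is not reproducible: the plan's own inputs give about 29 events where about 66 are needed, and about 45% power

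*SAP*

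**What the plan says.** SAP Section 6 bases its calculations on 500 participants, 250 per arm. For the severe-overdose endpoint it takes 38% of the assumed 20% control-arm overdose risk, "for a rate of 8 per 100 person-years in the control arm", and then claims at least 80% "power to detect a 50% reduction in the hazard of fatal overdose or ED visit for an overdose". Protocol Attachment F, section A1 (Power Calculation and Sample Size) makes the same claim and points to a Figure 6B in the funding application, which the Protocol's attachment list marks as not included. The SAP cites no figure. Neither document gives an event count, a formula or a significance level for this endpoint.

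The definition is not constant:
- SAP Section 6 applies the 38%, and so the rate of 8, to death or EMS attendance, but words the power claim for death or an ED visit.
- Protocol A1 assumes that "only 38% of self-reported overdoses would result in death or presentation to" the ED, so there the same rate belongs to death or ED.
- SAP Section 3 analyses an endpoint "defined as an EMS run for suspected overdose, an ED encounter for drug overdose, or drug overdose death".

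Follow-up differs as well. Protocol 3.1f compares this outcome "over the 12-month follow-up period in each group". SAP Section 3 censors "at the end of the follow-up period, defined as 15 months" after baseline and uses the same methods for the severe-overdose analysis. The SAP calls the endpoint exploratory; Protocol 3.1f calls it secondary.

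**The concern.** Time-to-event power depends on the number of events. A control rate of 8 per 100 person-years in 250 people followed for about a year means some 19 control events, and about half as many under the alternative. That is far too few for 80% power at a hazard ratio of 0.5.

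The cost lies in interpretation. A reader who accepts the stated power will treat a non-significant result for severe overdose as fairly strong evidence against a halving. At about 45% power a true halving would be missed more often than it was found, so such a result could not rule it out. Because the definition moves, it is also unclear which endpoint the claim covers.

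**Working it through.** **Inputs**
- 250 per arm, with up to 275 per arm if all 550 are enrolled; 80% retention (SAP Section 6).
- 1:1 allocation (Protocol 3.1a).
- Control rate λ = 0.08 per person-year; hazard ratio 0.5 (SAP Section 6).
- Follow-up t = 1 year (Protocol 3.1f) or 1.25 years (SAP Section 3).
- Two-sided 0.05. This is an assumption for this endpoint. The only level stated is in SAP Section 4, "to maintain the overall study power of 0.05, two-sided", where a significance level is evidently meant.

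**What reproduces.** The rate does: 0.38 × 0.20 = 0.076, rounded to 8 per 100. So does the primary claim. For 20% versus 10% with 200 per arm, power = Φ[(0.10 − 1.96·√(2·0.15·0.85/200)) / √((0.16 + 0.09)/200)] = Φ(0.849) = 80.2%.

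**Events needed (Schoenfeld).** 4(1.960 + 0.842)² / (ln 0.5)² = 65.3, so 66.

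**Events expected.** With exponential times, n(1 − e^(−0.08t)) + n(1 − e^(−0.04t)). For 250 per arm and one year this is 19.2 + 9.8 = 29.0.

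**Power.** Φ(√(29.0/4) × 0.693 − 1.96) = Φ(−0.093) = 46.3%. A simulated log-rank test gives 44.0%.

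**Variants** (hazard ratio 0.5, λ = 0.08; 10,000 simulated trials per row, 5,000 for the one-sided row):

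| Per arm | Follow-up | Events | Schoenfeld | Simulated |
|---|---|---|---|---|
| 250 | 12 months | 29.0 | 46% | 44% |
| 250, 20% exponential loss | 12 months | 26.0 | 42% | 40% |
| 200 (80% retained) | 12 months | 23.2 | 39% | 36% |
| 250 | 15 months | 36.0 | 55% | 53% |
| 200 (80% retained) | 15 months | 28.8 | 46% | 44% |
| 275 | 15 months | 39.6 | 59% | 57% |
| 275, one-sided 0.05 | 15 months | 39.6 | 70% | 68% |

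Counting events linearly in the last row (275 × 0.08 × 1.25 × 1.5 = 41.2) raises it only to about 72%.

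**What 80% would need**
- At a rate of 8: 65.3/0.1161 ≈ 563 per arm over 12 months, or 65.3/0.1439 ≈ 454 per arm over 15 months. The maximum enrolment is 550 in total.
- With 250 per arm: a control rate of about 19 per 100 person-years over 12 months, or about 15 over 15 months.
- With 250 per arm and a rate of 8: a hazard ratio of about 0.30 over 12 months (simulated power 79.5%) or 0.35 over 15 months (80.5%). Schoenfeld's formula gives 0.33 and 0.38, but simulated power there is only about 75%, so the simulated values are used.

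**A possible source, as conjecture only.** With the undiscounted 20 per 100 person-years, 250 per arm over 12 months gives 45.3 + 23.8 = 69.1 events and 82% power. The authors should check whether the 38% factor was carried into the calculation.

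**The case against.** Several points can fairly be made for the plan.

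- **The SAP's window is 15 months, so 53–55% is the fairer figure against it.** This stands for the SAP. The 12-month figure belongs to Protocol 3.1f and to the 12-month overdose risk from which the rate of 8 is derived. With 250 per arm, 15 months and no loss, a true halving is found slightly more often than missed. The statement that it would usually be missed holds at 12 months, or at 15 months with 80% retention.
- **The endpoint in SAP Section 3 is broader, so its rate may exceed 8.** Also true: power for that endpoint is unknown. To reach 80%, the rate would have to be roughly double the stated one (about 15 per 100 person-years at 15 months, 19 at 12), and no such figure is offered.
- **Figure 6B may contain other inputs, and no alpha is stated for this endpoint.** Neither can be checked. But the sample size, rate and effect are in the text beside the claim, the SAP does not rely on the figure, and one-sided testing also falls short.
- **Attrition may not matter for linked records.** Possibly, although Protocol 3.1e describes a separate consent for overdose records. The headline figure already assumes no loss, which favours the plan.
- **The endpoint is exploratory in the SAP.** This limits the consequence but does not make the stated power correct.

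**Conclusion.** The concern holds. With the stated 250 per arm, 8 per 100 person-years and a hazard ratio of 0.5, power at two-sided 0.05 is about 45% over 12 months and about 53–55% over 15 months, not at least 80%. Expected events fall short of those needed by a factor of about 2.3 at 12 months (65.3/29.0) and 1.8 at 15 months (65.3/36.0), too large a gap to come from rounding or choice of formula. No combination of the stated inputs reaches 80%.

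These figures assume exponential event times, proportional hazards, no attrition and the stated rate. Applying the plan's 80% retention lowers the 12-month figure to 36–39%. The primary endpoint's sample size is unaffected. This should be fixed, but it does not threaten the trial's main analysis.

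**What to change.** In SAP Section 6 and in Protocol Attachment F, section A1, replace the power claim for this endpoint with wording such as:

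> With 250 per arm, 8 first events per 100 person-years in controls, two-sided alpha 0.05 and no attrition, power for a hazard ratio of 0.5 is about 45% over 12 months and about 53% over 15 months. By simulation, the hazard ratio detectable with 80% power is about 0.30 over 12 months and 0.35 over 15 months. A non-significant result for this endpoint is not evidence of no effect.

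Use one endpoint definition throughout that paragraph, consistent with the severe-overdose endpoint in SAP Section 3, and give the control rate that belongs to it. If that rate is not 8 per 100 person-years, recompute the figures before inserting them.

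The cost is a text change in two documents and, if the rate changes, a short recalculation. A published figure becomes less favourable. No participants are added and the primary analysis does not change.
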